## **10.7 Secondary objective 6**

### **To evaluate the safety of eltrombopag.**

This objective has been resolved in this document with:

- Adverse events analysis (see section 9).
- Reason for study withdrawal (see section 7).

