Safety: To evaluate the safety of eltrombopag.	Occurrence, incidence, severity of adverse events (AEs), serious adverse events (SAEs) based on the CTCAE criteria (v 4.03), and reasons for withdrawal from the study including the AEs leading to discontinuation.	Refer to Section 10.5.2

Objective	Endpoint	Analysis
	Physical examination, performance status, height and weight, vital signs, safety laboratory evaluations, ECG and ophthalmological monitoring.	

4 Study design

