8.1 Adverse events

8.1.1 Definitions and reporting

An adverse event is defined as the appearance of (or worsening of any pre-existing) undesirable sign(s), symptom(s), or medical condition(s) that occur after patient's signed informed consent has been obtained.

Abnormal laboratory values or test results occurring after informed consent constitute adverse events only if they induce clinical signs or symptoms, are considered clinically significant, require therapy (e.g., hematologic abnormality that requires transfusion or hematological stem cell support), or require changes in study medication(s).

Adverse events that begin or worsen after informed consent should be recorded in the Adverse Events CRF. Conditions that were already present at the time of informed consent should be recorded in the Medical History page of the patient's CRF. Adverse event monitoring should be continued for at least 30 days (or 5 half-lives, whichever is longer) following the last dose of study treatment. Adverse events (including lab abnormalities that constitute AEs) should be described using a diagnosis whenever possible, rather than individual underlying signs and

symptoms. When a clear diagnosis cannot be identified, each sign or symptom should be reported as a separate Adverse Event.

Adverse events will be assessed according to the Common Terminology Criteria for Adverse Events (CTCAE) version 4.03.

If CTCAE grading does not exist for an adverse event, the severity of mild, moderate, severe, and life-threatening, corresponding to Grades 1-4, will be used. CTCAE Grade 5 (death) will not be used in this study; rather, information about deaths will be collected through a Death form

The occurrence of adverse events should be sought by non-directive questioning of the patient (subject) during the screening process after signing informed consent and at each visit during the study. Adverse events also may be detected when they are volunteered by the patient (subject) during the screening process or between visits, or through physical examination, laboratory test, or other assessments. As far as possible, each adverse event should be evaluated to determine:

1. The severity grade (CTCAE Grade 1-4).
2. Its duration (Start and end dates or ongoing).
3. Its relationship to the study treatment
4. Action taken concerning study or investigational treatment (none, dose adjusted, temporarily interrupted, permanently discontinued, unknown, not applicable)

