10.5.2.3 Laboratory abnormalities

For laboratory tests covered by the CTCAE version 4.03, the reporting team will grade laboratory data accordingly. For laboratory tests covered by CTCAE, a Grade 0 will be assigned for all non-missing values not graded as 1 or higher. Grade 5 will not be used.

For laboratory tests where grades are not defined by CTCAE version 4.03, results will be categorized as low/normal/high based on laboratory normal ranges.

The following summaries will be generated separately for hematology, biochemistry tests and urinary laboratory tests:

- Worst post-baseline CTCAE grade (regardless of the baseline status). Each patient will be counted only once for the worst grade observed post-baseline.
- Shift tables using CTCAE version 4.03 grades to compare baseline to the worst on treatment value.
- For laboratory tests where grades are not defined by CTCAE version 4.03, shift tables using the low/normal/high/ (low and high) classification to compare baseline to the worst on-treatment value.

In addition to the above-mentioned tables and listings, other exploratory analyses, for example figures plotting time course of raw or change in laboratory tests over time or box plots might be specified in the SAP and TLF shells.

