10.5.2.4 Other safety data

ECG

- The number (%) of patients with notable values will be presented; also, data on ECG results will be listed for all patients with at least one abnormality.

Vital signs

- Data on vital signs will be tabulated and listed, notable values will be flagged. The number (%) of patients with notable values will be presented.

Physical examination

- Shift table baseline to worst on-treatment result
- Table with descriptive statistics at baseline, one or several post-baseline time points and change from baseline to this/these post-baseline time points.

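### The SAP answers the safety objective with adverse events and withdrawal reasons only, and so omits the post-baseline laboratory, ECG, vital-sign and physical-examination summaries that the protocol specifies

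*SAP*

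**What the plan says.** **Protocol.** Beyond AEs and withdrawals, the safety endpoint in Table 3-1 covers "Physical examination, performance status, height and weight, vital signs, safety laboratory evaluations, ECG and ophthalmological monitoring". The analyses follow in section 10.5.2:

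- 10.5.2.1 assigns all safety analyses to the Safety Set.
- 10.5.2.3 asks, separately for hematology, biochemistry and urine, for each patient's worst post-baseline CTCAE grade and for "Shift tables using CTCAE version 4.03 grades to compare baseline to the worst on treatment value". Tests without a CTCAE grade get low/normal/high shift tables.
- 10.5.2.4 asks for the number and percentage of patients with notable ECG values, and adds that "data on ECG results will be listed for all patients with at least one abnormality". It also asks for tabulated and flagged vital signs, and a baseline-to-worst shift table for physical examination.

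**SAP.** Section 10.7 states "This objective has been resolved in this document with" two items: the AE analysis in section 9 and the withdrawal reasons in section 7. Section 4 runs only the AE analysis on the Safety Set and everything else on the Full Analysis Set. ECG, eye, Karnofsky, vital-sign, laboratory and blood-smear descriptions appear in section 6, whose heading limits it to the screening visit. The laboratory part (6.13) covers neutrophils, platelets, hemoglobin and immunosuppressant levels. It contains no ALT, AST or bilirubin.

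**The concern.** AE tables do not replace laboratory tables. Protocol 8.1.1 says "Abnormal laboratory values or test results occurring after informed consent constitute adverse events only if they induce clinical signs or symptoms", are considered clinically significant, need therapy, or lead to a change in study medication. Below that bar, a liver-test change is a laboratory value and nothing more.

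The protocol warns of severe and potentially fatal liver injury, requires liver tests at every visit (6.2.1.2), and names hepatobiliary and cataract-related events as AEs of special interest (8.1.3). In an open-label, single-arm study of 33 patients, graded laboratory data are the part of the safety result that depends least on investigators' judgment of what counts as an event. Patients may also enter with ALT/AST up to 3 x ULN (exclusion criterion 11), so a baseline-to-worst shift table is needed to separate change on drug from status at entry.

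**Working it through.** No power, alpha or sample-size figure is involved. The check sets the two documents side by side and then traces which liver-test results reach an SAP table.

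**Step 1: what the protocol specifies against what the visible SAP contains after baseline.**

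| Safety item | Protocol analysis | Visible SAP, post-baseline |
|---|---|---|
| AEs | 10.5.2.2 | Section 9 |
| Withdrawal reasons | Table 3-1; 10.4.3 | Section 7 |
| Safety laboratory | 10.5.2.3: worst grade, shift tables | None |
| ECG | 10.5.2.4: notable values, listing | None (6.9 is screening) |
| Vital signs | 10.5.2.4: tabulated, notable values | None (6.12 is screening) |
| Physical examination | 10.5.2.4: shift table | None at any visit |
| Eye examination | Endpoint in Table 3-1; no analysis in 10.5.2 | None (6.10 is screening) |
| Performance status | Endpoint in Table 3-1; no analysis in 10.5.2 | None (6.11 is screening) |

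The SAP does analyse some laboratory values after baseline: neutrophils, platelets and hemoglobin in 10.2. These are efficacy analyses.

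**Step 2: how much data is affected.** Liver tests are scheduled after baseline at weeks 1, 2, 3, 4, 6, 8, 10, 12, 16, 20, 24, 30, 36 and 40, which is 14 visits. With 33 patients that is at most 33 x 14 = 462 scheduled sets, fewer in practice because non-responders leave at week 16. ECG and eye examinations are repeated at week 24 and the final visit, at most 33 x 2 = 66 of each.

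**Step 3: which liver-test results become AEs.** The rule is 8.1.1 together with 8.1.2.1, which confirms that a protocol-required dose hold makes the abnormality an AE. Applying it to Table 6-3:

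- ALT/AST above 5 x ULN: interruption or discontinuation is mandatory, so it is an AE and reaches SAP section 9.
- ALT/AST above 3 and up to 5 x ULN: the dose is maintained, but treatment is discontinued if there are symptoms or decompensation, progressive increase, or persistence for 4 weeks or more. Any of these makes it an AE. Without them, and if untreated and not judged clinically significant, it need not be one.
- ALT/AST above ULN and up to 3 x ULN: the dose is maintained, and the same reasoning applies without the 4-week limit.
- Total bilirubin above 1.5 and up to 3 x ULN: dosing is interrupted, so it is an AE, unless the rise is indirect only. In that case no dose change is required and it need not be an AE.
- Combined rises meeting the criteria in 6.2.4, confirmed and without another cause: reported as serious AEs.

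**Result.** The results with no SAP table are mainly asymptomatic, non-progressive ALT/AST rises up to 5 x ULN (under 4 weeks if above 3 x ULN) and indirect-only bilirubin of 1.5 to 3 x ULN, where not treated or judged clinically significant.

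**The case against.** The case for the SAP has several parts.

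- **It follows one of the protocol's own statements.** Secondary objective 6 in the protocol summary says safety is assessed through AEs, serious AEs and AEs leading to discontinuation. SAP 10.7 largely mirrors that. This explains the omission but does not justify it: the same summary and Table 3-1 give the wider endpoint, and 10.5.2.3 and 10.5.2.4 specify the tables. The visible SAP does not say that it replaces them.
- **Important findings reach the AE tables anyway.** Significant new ECG and eye findings must be entered as AEs (7.3.2.7, 7.3.2.8). SAP 7 lists abnormal laboratory values and test results among the withdrawal reasons, and SAP 8 shows reasons for dose modifications. This stands, and it narrows the gap to findings below the AE bar.
- **Nothing has been withdrawn.** Protocol 10.5.2.2 still commits to listing all safety data, and 10.5.2.3 refers to table shells that are not among these documents. This also stands.
- **Parts of the SAP are blacked out** (6.8 and an entry after 10.7). They cannot be judged, but 10.7 is visible and gives its own scope in full.

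A reader might infer that liver-enzyme rises outside the AE definition would never be reported, or would go unreported in every patient. The documents do not support that: the listing commitment remains, and the affected range is bounded as shown above. A reader might also infer that the SAP drops a planned eye analysis. It does not, because protocol 10.5.2 never specifies one. What goes unanalysed is an endpoint.

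**Conclusion.** The point holds as a conflict between the two documents. The protocol's post-baseline safety-laboratory, ECG, vital-sign and physical-examination summaries have no counterpart in the visible SAP, and eye monitoring after baseline is summarised in neither document. For the liver, the loss is confined to lower-range changes that stay below the AE bar. They would be listed under the protocol but not tabulated under the SAP.

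The number of patients affected cannot be derived from the documents, which give no expected rate of such rises. The conclusion assumes that the blacked-out SAP entries do not contain these tables and that no table shells supply them.

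The Safety Set restriction in SAP 4 matters for scope more than for counts. Patients who consent but never start treatment are screen failures (protocol 7.2.1.2), so the Full Analysis Set and Safety Set should nearly coincide. The primary efficacy analysis is not touched. The correction should be made because it is cheap and restores analyses already promised for a stated endpoint.

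**What to change.** 1. Add to SAP 10.7, on the Safety Set, the tables of protocol 10.5.2.3 and 10.5.2.4: worst post-baseline CTCAE grade and baseline-to-worst shift for hematology, biochemistry and urine; low/normal/high shift for ungraded tests; notable ECG and vital-sign values; and the physical-examination shift table.
2. Amend SAP 4 so that the Safety Set serves all safety analyses, as protocol 10.5.2.1 requires.
3. Add a simple summary of the eye examinations at baseline against week 24 and the final visit. This is new, since the protocol names the endpoint without an analysis.
4. Optionally, count patients by ALT/AST multiple of ULN, with and without concurrent bilirubin elevation. This would be an addition and not a protocol table.

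If the sponsor does intend a reduced safety analysis, the SAP should say so and justify the departure from protocol 10.5.2. The cost is a few extra tables from data already collected. No visit, assessment or sample-size change is needed.
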